9.1.1 Pretreatment Phase

The Pretreatment Phase will last up to 28 days and will include a Screening Period and a Baseline Period.

9.1.1.1 Screening Period

Screening will occur between Day –28 and Day –2. The purpose of the Screening Period is to obtain informed consent and to establish protocol eligibility. Informed consent will be obtained after the study has been fully explained to each subject and before the conduct of

any screening procedures or assessments. Procedures to be followed when obtaining informed consent are detailed in [Section 5.3](#).

The Screening Disposition case report form (CRF) must be completed to indicate whether the subject is eligible to enroll in the study and to provide reasons for screen failure, if applicable.

The results of all screening assessments and evaluations must be completed and reviewed by the investigator prior to the Baseline Visit.

9.1.1.2 Baseline Period

The purpose of the Baseline Period is to confirm protocol eligibility as specified in the inclusion/exclusion criteria (as detailed in [Section 9.3.1](#) and [Section 9.3.2](#)). Results of baseline assessments must be obtained prior to the first dose of study treatment (Cycle 1 Day 1). Baseline assessments can be performed on Day -1 or on Cycle 1 Day 1 prior to start of study treatment.

Subjects who complete the baseline assessments and continue to meet the criteria for inclusion/exclusion ([Sections 9.3.1](#) and [9.3.2](#)) will begin the Treatment Phase.

9.1.2 Treatment Phase

The Treatment Phase will begin with the first dose of study drug administration in Cycle 1. The duration of the Treatment Phase is 1 cycle (4 weeks of treatment) in Phase 1 of the study, and 4 cycles (16 weeks of treatment) in Phase 2 of the study. Subjects will receive study treatment in 28-day cycles. Tumor assessments will be performed during the Treatment Phase at Week 4 \pm 1 week (Phase 1) and at Week 8 \pm 1 week and Week 16 \pm 1 week (Phase 2).

Subjects who discontinue study treatment during Cycle 1 (Phase 1), or before completing 4 cycles of treatment (Phase 2), will transition to the Off-treatment Visit.

9.1.3 Extension Phase

All subjects who are still on study treatment following completion of Cycle 1 in Phase 1, or after completing 4 cycles in Phase 2 of the study, will transition to the Extension Phase. During the Extension Phase, subjects will continue to receive the same study treatment in 28-day cycles. Tumor assessments will be performed during the Extension Phase at Week 12 \pm 1 week and Week 24 \pm 1 week, and every 12 weeks \pm 1 week thereafter (Phase 1) and at Week 24 \pm 1 week, and every 12 weeks \pm 1 week thereafter (Phase 2).

9.1.4 Treatment Discontinuation Criteria

Subjects may remain on study treatment as long as they do not meet any of the following criteria: 1) experience objective progression of disease (according to Response Evaluation Criteria in Solid Tumors [RECIST] 1.1 or Response Assessment in Neuro-Oncology

[RANO] criteria, as appropriate), 2) exhibit no clinical benefit (in the opinion of the investigator), 3) experience unacceptable toxicity leading to withdrawal from the study, 4) withdraw or are withdrawn from the study for any reason, or, 5) termination of the study program.

As long as the subject has not experienced intolerable toxicity, he or she can continue to receive study treatment.

9.1.5 Off-Treatment Visit

After subject discontinues treatment, an Off-Treatment Visit and the procedures noted in the Schedule of Assessments ([Table 7](#) and [Table 8](#)) should be completed within 28 days after the last dose of study treatment.

9.1.6 Post-Treatment Phase

9.1.6.1 Follow-Up Period

The post-treatment follow up will begin when the subject discontinues study treatment and all off-treatment assessments have been completed. Subjects who discontinue study treatment for reasons other than disease progression will be followed for documented disease progression for 1 year or until another anticancer therapy is initiated whichever occurs first. Subjects will be followed for survival every 3 months until death or for 1 year, whichever occurs first, unless the study is terminated or if the subject discontinues due to withdrawal of consent or is lost to follow up.

After data cutoff, tumor assessments may be performed as clinically indicated using the institutional guidelines, following the prevailing local standard of care.

As required by some regulatory agencies, the following estimates are provided:

- The study is planned to begin in April 2017 and to end in March 2022.
- The maximum estimated period for each subject on study is anticipated to be approximately 2 years (24 treatment cycles). However, subjects will continue to receive study treatment as long as they demonstrate clinical benefit.

9.2 Discussion of Study Design

This multicenter, open-label, Phase 1/2 study will investigate safety, tolerability and antitumor activity of lenvatinib in combination with everolimus in pediatric subjects with relapsed or refractory solid tumors.

The Phase 1 portion of the study utilizes dose-finding rolling 6 design ([Skolnik, et al., 2008](#)), which allows enrollment of more than 3 subjects at the particular dose level, unlike the traditional 3+3 Phase 1 study design. If there is no DLTs in the first 3 subjects enrolled under rolling 6 design, then the fourth subject can be allocated to the next higher dose level. If toxicity data are not available on the first 3 subjects, or if one DLT is observed, in which

case the new subject will be kept at the same dose level. The main advantage of the rolling 6 design is the reduction of the overall study duration as it aims to decrease the number of times the study is suspended to accrual.

The Simon-optimal 2-stage design utilized for Phase 2 portion of the study allows for interim evaluation for futility. The traditional single-stage study designs evaluate drug response rate on the predetermined number of subjects, possibly unnecessarily exposing children to the risk of ineffective new agents. For ethical reasons, Simon's 2-stage design utilizes a small number of subjects to determine drug activity and allows early termination of the study if activity criteria are not met. This prevents exposure of too many pediatric subjects to an inactive study drug.

Toxicity will be assessed according to National Cancer Institute's CTCAE v4.03. In this study, the subjects will remain on treatment as long as they do not experience progression of disease or unacceptable toxicity. This will allow evaluation of short-term toxicity, as well as, side effects after prolonged use of combination of lenvatinib and everolimus, which is particularly important for pediatric population where physical growth and tissue maturation continues.

9.3 Selection of Study Population

A maximum accrual of 120 subjects in Phase 1 and Phase 2 portions of the study is expected at approximately 60 sites (20 sites for the Phase 1 portion and an additional 40 sites for the Phase 2 portion).

Phase 1: 4 to 48 evaluable subjects. In the event that each of the Dose Levels -1, 1, 2, and 3 is expanded to 12 subjects, a maximum of 54 subjects (allowing for 20% to be non-evaluable and including the additional 6 subjects for PK analysis) will be enrolled.

Phase 2 Cohorts 1 to 3: 10 to 20 evaluable subjects per cohort (maximum 22 subjects per cohort allowing for 10% to be non-evaluable). A maximum of 66 subjects will be enrolled in Phase 2. In each cohort, at least 50% of the subjects enrolled will be <18 years old at the time of informed consent.

Subjects who do not meet all of the inclusion criteria or who meet any of the exclusion criteria will not be eligible to receive study treatment.

9.3.1 Inclusion Criteria

Subjects must meet all of the following criteria to be included in this study:

1. Histologically or cytologically confirmed diagnosis of the following tumor types:
 - a. Phase 1: Recurrent or refractory solid tumors (excluding hepatoblastoma and lymphomas), including primary CNS tumors; subjects must have either measurable or evaluable disease. Subjects with diffuse intrinsic pontine glioma, optic pathway glioma, or pineal tumors with elevated tumor markers (alpha-fetoprotein [AFP] and

- beta-human chorionic gonadotropin [β -hCG] [or hCG]) do not require histological or cytological confirmation of diagnosis.
- b. Phase 2 : Recurrent or refractory tumors; subjects must have measurable disease
 - Cohort 1: Ewing sarcoma/pPNET
 - Cohort 2: Rhabdomyosarcoma
 - Cohort 3: HGG (subjects with Diffuse Intrinsic Pontine Glioma are not eligible)
2. Measurable disease that meets the following criteria (Phase 2):
- a. RECIST 1.1 (for all tumor types except HGG)
 - At least 1 lesion of ≥ 1.0 cm in the longest diameter for a non lymph node or ≥ 1.5 cm in the short-axis diameter for a lymph node which is serially measurable according to RECIST 1.1 using computed tomography /magnetic resonance imaging (CT/MRI).
 - b. Response Assessment in Neuro-Oncology (RANO) for high grade glioma (HGG) ([Wen, et al., 2010](#))
 - At least one lesion must be measurable as defined as a bi-dimensionally contrast-enhancing lesion with clearly defined margins by CT or MRI scan, with a minimal diameter of 1 cm, and visible on 2 axial slices which are preferably at most 5 mm apart with 0 mm skip.

Lesions that have had external beam radiotherapy (EBRT) or locoregional therapies such as radiofrequency (RF) ablation must show evidence of progressive disease based on RECIST 1.1 to be deemed a target lesion.

3. Karnofsky performance score ≥ 50 for subjects >16 year of age and Lansky play score ≥ 50 for subjects ≤ 16 years of age. Note: Neurologic deficits in subjects with CNS tumors must have been relatively stable for at least 7 days prior to study enrollment. Subjects who are unable to walk because of paralysis, but who are up in a wheelchair, will be considered ambulatory for the purpose of assessing the performance score.
4. Subjects must have fully recovered from the acute toxic effects of all prior anti-cancer therapy and must meet the following minimum duration from prior anti-cancer directed therapy prior to enrollment. If after the required timeframe, the numerical eligibility criteria are met, eg, blood count criteria, the subject is considered to have recovered adequately.
 - a. Cytotoxic chemotherapy or other chemotherapy known to be myelosuppressive: ≥ 21 days after the last dose of cytotoxic or myelosuppressive chemotherapy (42 days if prior nitrosourea).
 - b. Anti-cancer agents not known to be myelosuppressive (eg, not associated with reduced platelet or absolute neutrophil counts): ≥ 7 days after the last dose of agent.
 - c. Monoclonal antibodies: ≥ 21 days or 3 half-lives (whichever is shorter) of the antibody must have elapsed after the last dose of a monoclonal antibody (including immune checkpoint inhibitors). ([Appendix 3](#)). Toxicity related to prior antibody therapy must be recovered to Grade ≤ 1 .
 - d. Corticosteroids: If used to modify immune adverse events (AEs) related to prior therapy, ≥ 14 days must have elapsed since last dose of corticosteroid. Subjects

- receiving corticosteroids, who have not been on a stable or decreasing dose of corticosteroid for at least 7 days prior to enrollment, are not eligible.
- e. Hematopoietic growth factors: ≥ 14 days after the last dose of a long-acting growth factor (eg, Neulasta) or 7 days for short-acting growth factor. For agents that have known AEs occurring beyond 7 days after administration, this period must be extended beyond the time during which AEs are known to occur.
 - f. Interleukins, interferons, and cytokines (other than hematopoietic growth factors): ≥ 21 days after the completion of interleukins, interferons or cytokines (other than hematopoietic growth factors).
 - g. Stem cell infusions (with or without total body irradiation [TBI]):
 - Allogeneic (non-autologous) bone marrow or stem cell transplant, or any stem cell infusion including donor leukocytes infusion or boost infusion: ≥ 84 days after infusion and no evidence of graft versus host disease (GVHD).
 - Autologous stem cell infusion including boost infusion: ≥ 42 days
 - h. Cellular Therapy: ≥ 42 days after the completion of any type of cellular therapy (eg, modified T cells, natural killer cells, dendritic cells, etc).
 - i. Radiotherapy (XRT)/External Beam Irradiation including Protons: ≥ 14 days after local XRT; ≥ 150 days after total body irradiation, craniospinal XRT or if radiation to $\geq 50\%$ of the pelvis; ≥ 42 days if other substantial bone marrow radiation.
 - j. Radiopharmaceutical therapy (eg, radiolabeled antibody, iodine-131 metaiodobenzylguanidine [^{131}I -MIBG]): ≥ 42 days after systemically administered radiopharmaceutical therapy.
 - k. VEGF/VEGFR-targeted or mTOR-targeted therapies:
 - Must not have received prior exposure to lenvatinib
 - May have previously progressed on an mTOR inhibitor
 - No more than 2 prior VEGF/VEGFR-targeted therapies (For Phase 2 only)
 - Must not have received prior VEGF/VEGFR-targeted therapy in combination with an mTOR inhibitor (For Phase 2 only)
5. Male or female subjects must be ≥ 2 years and < 18 years of age for enrolment in Phase 1 or ≥ 2 years and ≤ 21 years of age for enrolment in Phase 2.
6. Adequate bone marrow function:
- For subjects with solid tumors without known bone marrow involvement:
 - Peripheral absolute neutrophil count (ANC) $\geq 1000/\text{mm}^3$
 - Platelet count $\geq 100,000/\text{mm}^3$
 - Hemoglobin ≥ 8.0 g/dL at baseline (may receive red blood cell transfusions)
 - For subjects with known bone marrow metastatic disease:
 - Peripheral ANC $\geq 1000/\text{mm}^3$
 - Platelet count $\geq 100,000/\text{mm}^3$ (and with no platelet transfusions for at least 7 days prior to enrollment)
 - May receive transfusions provided they are not known to be refractory to red cell or platelet transfusions. These subjects will not be evaluable for hematologic

toxicity. At least 5 of every cohort of 6 subjects with a solid tumor must be evaluable for hematologic toxicity, for the dose-escalation part of the study. If dose-limiting hematologic toxicity is observed, all subsequent subjects enrolled must be evaluable for hematologic toxicity.

7. Adequate renal function:

- Creatinine clearance or radioisotope glomerular filtration rate (GFR) ≥ 70 mL/min/1.73 m² or
- A serum creatinine based on age/gender as follows:

Age	Maximum Serum Creatinine (mg/dL)	
	Male	Female
2 to <6 years	0.8	0.8
6 to <10 years	1	1
10 to <13 years	1.2	1.2
13 to <16 years	1.5	1.4
≥ 16 years	1.7	1.4

The threshold creatinine values in this table were derived from the Schwartz formula for estimating GFR utilizing child length and stature data published by the Centers for Disease Control and Prevention (CDC).

- Urine dipstick <2+ for proteinuria. Subjects who have $\geq 2+$ proteinuria on dipstick urinalysis should undergo a spot protein-creatinine (P/C) ratio that should be Grade <2 per CTCAE v4.03, and if possible, perform a 24-hour urine collection (children and adolescents ≤ 12 years of age must have ≤ 500 mg of protein/24 hours and subjects >12 years of age must have ≤ 1 g of protein/24 hours).

8. Adequate liver function:

- Bilirubin (sum of conjugated + unconjugated) $\leq 1.5 \times$ upper limit of normal (ULN) for age, except for unconjugated hyperbilirubinemia of Gilbert’s syndrome.
- ALT and AST $\leq 3 \times$ ULN
- Serum albumin ≥ 2 g/dL

9. Adequate cardiac function:

- Adequate cardiac function as evidenced by left ventricular shortening fraction of $\geq 27\%$ by echocardiogram or left ventricular ejection fraction (LVEF) $\geq 50\%$ at baseline, as determined by echocardiography/multigated acquisition (MUGA) scan.
- QT interval corrected for heart rate using Fridericia’s formula (QTcF) ≤ 480 msec.

10. Adequate neurologic function:

- Subjects with seizure disorder may be enrolled if on non-enzyme-inducing anticonvulsants and well controlled.
- Nervous system disorders (CTCAE v4.03) resulting from prior therapy and not tumor-induced must be \leq Grade 2.

11. Adequate BP control with or without antihypertensive medications, defined as: A BP < the 95th percentile for sex, age and height/length ($\leq 150/90$ mmHg for subjects aged 18 - 21 years) at Screening (as per National Heart Lung and Blood Institute [NHLBI] guidelines; [Appendix 7](#) and [Appendix 8](#)) and no change in antihypertensive medications within 1 week prior to Cycle 1 Day 1.

12. Adequate coagulation:
 - International Normalized Ratio (INR) ≤ 1.5
13. Adequate pancreatic function:
 - Serum amylase $\leq 1.5 \times \text{ULN}$
 - Serum lipase $\leq 1.5 \times \text{ULN}$
14. Adequate metabolic function:
 - Serum triglycerides $\leq 300 \text{ mg/dL}$
15. Adequate glycemic control defined as:
 - Fasting serum glucose $\leq 160 \text{ mg/dL}$
16. Subjects must have a minimum BSA of 0.6 m^2 at study entry.

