7 INTRODUCTION

Solid tumors make up about 30% of all cancers in children. Current strategies for treatment of solid tumors in children have greatly improved in the last few decades. The success of curing nearly 80% of children diagnosed with cancer is tempered by the inability to cure the remaining 20% with conventional approaches. There remains a significant unmet medical

need for more effective treatment options with a manageable safety profile and for identifying biomarkers to more accurately diagnose these tumors and determine the level of risk in pediatric patients with solid tumors.

Some of the most common types of solid tumors found in children are brain tumors, rhabdomyosarcoma, and Ewing sarcoma/peripheral primitive neuroectodermal tumor (pPNET).

High grade gliomas (HGGs) represent approximately 8–12% of all pediatric central nervous system (CNS) tumors. The overall total incidence of HGG (including anaplastic astrocytoma, anaplastic oligodendrioglioma, glioblastoma, mixed glioma, and malignant glioma) among children 0-19 years old is approximately 0.85 per 100,000 (CBTRUS 2012). The distribution of HGGs between males and females is relatively equal (Finlay, et al., 2005). Pediatric HGGs are very aggressive and malignant lesions. Initial treatment strategies typically consist of a gross total resection when feasible followed by focal radiotherapy combined with chemotherapy. Despite improvements in neurosurgery, radiotherapy, and chemotherapy, the outcome for children with HGG remains poor. No effective chemotherapy regimens have been identified for any pediatric HGG (MacDonald, et al., 2011). Two-year survival rates range from 10% to 30%.

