Appendix 14 Response Assessment in Neuro-Oncology (RANO) Criteria

The RANO guidelines are as follows:

Specific lesions are to be evaluated serially with comparative analysis of changes in the area of contrast enhancement, as well as the non-enhancing component will be performed. The product of the maximal cross sectional enhancing diameters will be used to determine the size of the contrast-enhancing lesions as follows:

- **Measurable disease** is defined as bidimensionally contrast-enhancing lesions with clearly defined margins by CT or MRI scan, with a minimal diameter of 1 cm, and visible on 2 axial slices which are preferably at most 5 mm apart with 0 mm skip.
- **Non-measurable disease** is defined as either unidimensionally measurable lesions, masses with margins not clearly defined, or lesions with maximal perpendicular diameters <1cm. If there are multiple contrast-enhancing lesions, a maximum of 5 of the largest lesions may be measured and the sum of the products of the perpendicular diameters of these lesions determined.
- For subjects with recurrent disease who have **multiple lesions** of which only 1 or 2 are increasing in size, the enlarging lesions should be considered the target lesions for evaluation of response.
- Given the difficulty of differentiating “**pseudoprogression**” from true progression in the first 3 months after irradiation, subjects in this window should only be classified as progressive disease if the progression is outside the radiation field (beyond the high dose region or 80% isodose line) or if there is pathologic confirmation of disease progression.
- **Radiographic response** should be determined in comparison to the tumor measurement obtained at pretreatment baseline for determination of response, and the smaller of baseline or the smallest tumor measurement following initiation of therapy (nadir) for determination of progression:
 - Complete Response (CR): Complete disappearance of all enhancing measurable and non-measurable disease sustained for at least 4 weeks. In the absence of a confirming scan at least 4 weeks later, this scan will be considered only stable disease. No new lesions. Stable or improved non-enhancing (T2/FLAIR) lesions. Subjects must be on no corticosteroids and stable or improved clinically.

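### For irradiated HGG lesions, inclusion criterion 2 tests progression by RECIST 1.1, in conflict with the RANO three-month in-field rule in Appendix 14, so a lesion RANO would not call progressive can become a target.

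*Protocol*

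**What the plan says.** **Which criteria apply.** Criterion 2 in Protocol 9.3.1, repeated in the synopsis, has two branches for Phase 2. Branch 2a is headed "RECIST 1.1 (for all tumor types except HGG"), and branch 2b gives HGG to RANO. An unindented sentence after both branches covers lesions that have had external beam radiotherapy or locoregional therapy: they "must show evidence of progressive disease based on RECIST 1.1 to be deemed a target lesion". It names no tumour type, time since radiotherapy, radiation field or pathology condition.

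**Time since radiotherapy.** Criterion 4i, under "Radiotherapy (XRT)/External Beam Irradiation including Protons", requires at least "14 days after local XRT". A longer interval applies in other settings ("150 days after total body irradiation, craniospinal XRT or if radiation to" at least half of the pelvis). Protocol Section 7 describes usual HGG treatment as "gross total resection when feasible followed by focal radiotherapy combined with chemotherapy", so local radiotherapy is the setting to expect in Cohort 3.

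**The RANO rule.** Appendix 14 notes that pseudoprogression is hard to tell "from true progression in the first 3 months after irradiation". It therefore says that "subjects in this window should only be classified as progressive disease if the progression is outside the radiation field", or if pathology confirms it. Protocol 9.5.1.3.1 and Table 8 footnote q apply RANO to HGG tumour assessments, including those at Screening.

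**The decision rule.** Each Phase 2 cohort stops if there are no responses among the first 10 evaluable subjects, and fails with 2 or fewer among 20 (Protocol 9.1). The stated null rate is 5%, with one-sided alpha 0.07 and 88% power at 25% (Protocol 9.7.2, SAP 4). Response is read by the investigator, without independent assessment (SAP 5.4.1.2).

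**The concern.** Between day 14 and about 3 months after local radiotherapy, the eligibility text and the response criteria disagree on what counts as progression in an irradiated glioma. A lesion enlarging inside the field can meet the RECIST 1.1 test in criterion 2 while Appendix 14 would decline to call it progressive.

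Appendix 14 makes enlarging lesions the targets when there are several, and measures response against the pretreatment baseline. If such an enlargement were a radiation effect that later resolved, the shrinkage could be scored as a partial response with no contribution from the drugs.

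The cohort is single-arm and investigator-read, with a pass mark of 3 responses in 20, so there is little margin. One such response in stage 1 is also enough to prevent the futility stop.

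**Working it through.** **1. Set the rules side by side for HGG.**

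| Source | Test for an irradiated lesion | Time condition | In-field or pathology condition |
|---|---|---|---|
| Criterion 2, closing sentence | RECIST 1.1 progression | none | none |
| Criterion 4i | none (washout only) | 14 days after local, 150 days after craniospinal radiotherapy | none |
| Appendix 14 | RANO progression | special rule for first 3 months | outside the field, or pathologic confirmation |

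For local radiotherapy the rules conflict from day 14 to about day 91. After craniospinal radiotherapy the 150-day interval already exceeds 3 months, so they do not.

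**2. Reproduce the plan's operating characteristics.** The probability of passing at response rate p is

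R(p) = sum over x = 1 to 10 of Bin(x; 10, p) × P[Bin(10, p) ≥ max(0, 3 − x)].

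At p = 0.05:
- x = 1: 0.3151 × 0.0861 = 0.0271
- x = 2: 0.0746 × 0.4013 = 0.0299
- x ≥ 3: 0.0115
- total: R = 0.0686, which is the stated 0.07

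At p = 0.25, R = 0.882, the stated 88%. The chance of stopping at stage 1 under the null is 0.95^10 = 0.599.

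**3. Add unaided regression.** Let f be the share of HGG subjects who enter on an in-field lesion within 3 months of radiotherapy. Let s be the share of those whose lesion regresses to a confirmed PR without drug effect. The documents give neither, so both are assumptions. With a true response rate of 5%, the observed rate is p = 0.05 + 0.95 × f × s.

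| f | s | p | R(p) |
|---|---|---|---|
| 0 | 0 | 0.0500 | 0.069 |
| 5% | 5% | 0.0524 | 0.077 |
| 5% | 10% | 0.0548 | 0.085 |
| 10% | 10% | 0.0595 | 0.103 |
| 20% | 20% | 0.0880 | 0.235 |
| 30% | 30% | 0.1355 | 0.488 |

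**4. A figure that needs neither f nor s.** Suppose exactly one of the 20 subjects is a false responder, placed at random across the two stages, and the other 19 respond at 5%. The chance of passing is then 0.224, and with two false responders it is 0.555. These figures are conditional: they show how sensitive the rule is, not how often the situation arises.

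**The case against.** The strongest reply is that RANO already reaches entry. A reader of criterion 2 alone might infer that Appendix 14 governs only on-study scans. The documents do not support that: Protocol 9.5.1.3.1 and Table 8 footnote q apply RANO to HGG at Screening, and Appendix 14 contains a target-selection rule. A site that follows those sections would apply the three-month rule. This stands, and it makes the problem a contradiction between sections rather than a missing safeguard.

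A reader might also infer that RECIST progression is enough to make a lesion a target. It is a necessary condition only. The tumour must also be recurrent or refractory (1b) and RANO-measurable (2b), and the 14 days in 4i is a washout, not a rule for choosing targets. This stands too, but none of these conditions refers to field or pathology, so they do not close the gap.

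The closing sentence could be read as belonging to branch 2a. Criterion 2 would then set no progression test at all for irradiated HGG lesions, so the inconsistency with Appendix 14 would still need resolving.

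On size, Appendix 14 says that pseudoprogression is hard to distinguish; it does not say that such lesions shrink unaided to a PR. A PR needs a decrease of at least 50% sustained for 4 weeks, no new lesions, stable or improved T2/FLAIR, no corticosteroid increase and clinical stability. These conditions make s smaller, although a sustained resolution in a stable child could meet them. The objection to any firm estimate of inflation stands.

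**Conclusion.** The contradiction is in the current text. Criterion 2 names RECIST 1.1 for a judgement that the protocol elsewhere gives to RANO in HGG, and the two can disagree for up to about 3 months after local radiotherapy. A site following criterion 2 literally could choose a target that the trial's own response criteria would not call progressive, and later shrinkage could count as response.

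The effect on the Cohort 3 error rate is unknown. Over assumed values of f and s from 5% × 5% to 30% × 30%, the false-pass chance runs from about 8% to 49%, against 6.9% as designed. The upper end requires both assumptions at their maximum; at the lower end the change is negligible. A reader might infer that the HGG go rule is shown to be materially compromised, but the documents do not support that, because they give neither the share of subjects in the window nor any regression rate. What is established is an inconsistent eligibility rule feeding a decision that a single false response can move appreciably. It is worth correcting.

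**What to change.** **Protocol.** Reconcile criterion 2 (9.3.1 and synopsis), criterion 4i, Section 9.5.1.3.1, Table 8 footnote q and Appendix 14. The irradiated-lesion sentence should refer HGG to the RANO criteria the protocol already uses and keep RECIST 1.1 for the other tumours. No new clinical rule or washout is proposed.

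**SAP.** Add a sensitivity ORR at Week 16 for Cohort 3, excluding subjects with brain radiotherapy within 3 months before first dose. SAP 5.2.4 already summarises radiotherapy site (brain is a category) and time from the most recent radiotherapy to first dose. It does not list whether the target lesion lay in the field, so the exclusion cannot be limited to in-field lesions. It will also remove some subjects whose progression was out of field and acceptable under Appendix 14.

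**Cost.** One sentence of protocol text and one table. HGG entry may be slightly slower at sites that had relied on the RECIST wording, which matters in a disease with the poor survival described in Section 7. With at most 20 evaluable subjects the sensitivity estimate will be imprecise, so it should be read as a check on the primary result and not as a second decision rule. If it is too late to amend entry, the sensitivity table can still be produced.
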